3.7.3. Laboratory Measurements

Chemistry including thyroid panel and inflammatory, hematology, coagulation, and urinalysis (result, change and percent change from baseline) will be summarized by each treatment group and each post-baseline visit. Listing of laboratory assessments in Chemistry, Hematology and urinalysis will be provided. Local laboratory data will also be provided in the listings separately.

For alanine aminotransferase (ALT) and aspartate aminotransferase (AST), the number and percent of subjects with post-Baseline results falling in each of the following categories (using available central and local laboratory assessments) will be tabulated:

ALT or AST $> 3 \times ULN$, confirmed

ALT or AST $> 5 \times ULN$, confirmed

ALT or AST $> 3 \times$ ULN and serum total bilirubin $> 2 \times$ ULN, confirmed or INR > 1.5

ALT > 3 × ULN at any time during post-baseline or AST > 3 × ULN at any time during post-Baseline and with total bilirubin (TBL) > 2 × ULN at any time during post-baseline

For potassium (K), the number and percent of subjects falling in each of the following categories (using available central and local laboratory assessments) during post-baseline will be tabulated:

- Absolute levels $\geq 5.5 < 6$ mmol/L, confirmed
- Absolute levels \geq 6 mmol/L, confirmed

For platelet, the number and percentage of patients falling in each of the following categories (using available central and local laboratory assessments) based on post-baseline assessments will be provided:

- Confirmed Platelet count 75,000 to ≤ 100,000/mm³
- Confirmed Platelet count 50,000 to < 75,000/mm³
- Confirmed Platelet count 25,000 to < 50,000/mm³
- Confirmed Platelet count < 25,000/mm³
- Confirmed ≥ 30% Platelet count decrease from baseline; further classifying by the lower limit of normal (Above or below)

The number and percent of subjects with post-baseline results falling in the following categories (using available central and local laboratory assessments) will be also tabulated:

- Confirmed 30% decline in eGFR from Baseline eGFR values [eGFR should be calculated using the CKD-EPI creatinine equation (Levey et al. 2009)]
- Confirmed proteinuria: Absolute UPCR value ≥ 1000 mg/g

A confirmed value is based on a consecutive lab value performed on a different day to, but within 7 days of, the initial value. If there are multiple results on the same day, no matter from the same lab vendor or different lab vendors, then the worst value will be utilized in the analysis. If the repeated value is in the same or worse category, then the initial value is considered confirmed. If the consecutive value is in a better category, then the initial value is confirmed using the consecutive value category. If values that are not confirmed due to failure to retest or missing lab values, then the initial value is presumed confirmed.

Additional analysis to explore the possible thrombocytopenia incidence can also be found in AESI described in Section 3.7.2.

Subjects with more than one confirmed value will be counted exactly once under the worst confirmed category.

3.7.4. 2.12.4 Vital Signs

Vital signs include heart rate, respiratory rate, body temperature, BMI and systolic and diastolic blood pressure. Except for systolic and diastolic blood pressure, which are efficacy endpoints for this study and will be summarized separately, other vital signs will be summarized by treatment group for vital sign values as well as the change and percent change from baseline at each post-Baseline visit.

3.7.5. 12-Lead Electrocardiograms (ECG)

Safety 12 lead ECG will be performed at the visits indicated in the protocol Schedule of Procedures.

The ECG data will include ventricular rate (VR), PR interval, QRS duration, QT, and corrected QT intervals (QT corrected using the Fridericia's formula), and overall interpretation.

For the continuous variables above, descriptive statistics (n, mean, standard error, standard deviation, median, 25th percentile, 75th percentile, minimum and maximum) of results at study screening and study Week 13 visit, as well as the change and percent change from Baseline, will be presented in summary tables; for the categorical responses to overall interpretation.

All the ECG data collected will be listed.

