8.5.2. Safety Monitoring Rules for Platelet Count Results

Please refer also to Table 5.

Platelet count will be monitored every 2 weeks during the Treatment Period and at the following visits in the Post-Treatment Period: Study Days 85, 92, 106, 120, 148, and 169. The Investigator should review all platelet count results within 48 hours of receipt. If a patient's platelet count falls to 100,000/mm³ or less, then the patient's platelet counts should be monitored as described in Table 5. In case of platelet reduction to < 50,000/mm³, the platelet monitoring rule defined in Stopping rules (Section 8.6.3) should be followed.

Treatment should be held if there is no evaluable platelet count within 18 days prior to the scheduled dose. Any uninterpretable platelet count result must be rechecked and determined not to have met a stopping rule before dosing can continue. If Day 1 results are uninterpretable, Day 8 dosing may proceed, however, an interpretable result is required (and must be reviewed) before study drug dosing on Day 15.

In the event of a platelet count < 75,000/mm³, additional laboratory investigations may be conducted after discussion between the Investigator and the Sponsor Medical Monitor including: fibrinogen or D-dimer (local lab), complement (total C3, total C4, C5a), peripheral smear, citrated sample for platelets, CBC with reticulocytes and mean platelet volume, coagulation panel (prothrombin time/international normalized ratio [PT/INR], activated partial thromboplastin time [aPTT]), total globulins [IgG and IgM]), serology for hepatitis B virus, HCV, HIV (if not done at Screening), anti-platelet antibodies (specialty lab), and anti-drug antibodies (specialty lab).

Any case of a platelet count < 50,000/mm³ should be reported to the Sponsor in an expedited fashion (see Section 9.3.4). The Study Medical Monitor will discuss the assessment and treatment of such subjects with the Investigator.

Table 5: Monitoring Schedule and Stopping Rules for Platelet Counts

Platelet Count on Rx	Drug Dose	Monitoring
> 100,000/mm ³	No action	Monitor per Schedule of Procedures (Appendix A)
$\geq 75,000-$ $\leq 100,000/\text{mm}^3$	No action	Monitor every week until 3 successive values > 100,000/mm ³

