APPENDIX A. SCHEDULE OF PROCEDURES

Appendix A Schedule of Procedures

	Scree	n	Treati (12 W		Period										Post-Treatm (13 Weeks)	nent Pe	riod			
Study Week			Wk1	Wk2	Wk3	Wk4	Wk5	Wk6	Wk7	Wk8	Wk9	Wk10	Wk11	Wk12	Wk13	Wk14	Wk16	Wk18	Wk22	Wk25
Study Day	D-42 D-1	to	D1	D8	D15	D22	D29	D36	D43	D50	D5 7	D64	D71	D78	Treatment Early Term ⁹ /D85	D92	D106	D120		PT Early Term ⁹ / D169
Visit Window (Days)	NA		NA	± 2	± 2	± 2	± 2	± 2	± 2	± 2	± 2	± 2	± 2	± 2	± 2	± 2	± 2	± 5	± 5	± 5
Scheduled Visit #	1	2	3	4	5	6	7	8	9	10	11	12	13	14	15	16	17	18	19	20
Option for Home Health Care Visit ¹⁰				X	X	X	X	X	X	X	X	X	X	X ¹⁴		X ¹⁴	X	X	X	
Informed Consent	X																			
Inclusion/Exclusion	X	X	Xa																	
Medical History	X																			
Hydration and Low Sodium Diet Education	X	←	Continuous Counseling & Monitoring																	
CVD Risk Factors	X																			
Body Weight and Height ⁸	X		X												X					X
Physical Exam ¹	X		X												X					X
ECG (12-Lead)	X														X					
EQ-5D-5L, SF-12, POP-HSQ ¹⁵			X						X						X		X			
PGI-S ¹⁵			X												X					
PGI-C ¹⁵															X					
HTN Medication Compliance			X	X	X.	X	X	X	X.	X	X	X	X	X	X	X	X	X	X	X
Vital Signs (clinic) ²	X	X	Xa	Xa	Xª	Xª	Xª	Xª	Xª	Xª	Xª	Xª	Xa	Xa	X	X	X	X	X	X
HIV, Hep B & C	X																			
FSH ³	X																			
Pregnancy Test.4	X																			
Chemistry Panel ^{7, 10}	X		Xª		Xª		Xª		Xª		Xª		Xª		X	X	X	X	X	X
Archived Urine Sample.6	X		Xª				Xª				Xª				X	X	X	X	X	X
TSH, FT3, FT4	X																			
Hematology. ⁷	X		Xª		Xª		Xª		Xª		Xª		Xª		X	X	X	X		X
Urinalysis. ¹⁰	X^{16}		Xª		Xª		Xª		Xª		Xª		Xa		X	X	X	X	X	X

Amendment 4 4 November 2021

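### The confirmed ≥ 30% platelet-decrease row in SAP 3.7.3 relies on a 7-day follow-up count that neither the visit schedule nor any retest rule supplies while the count stays above 100,000/mm³

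*Combined protocol and SAP*

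**What the plan says.** SAP 3.7.3 (Laboratory Measurements) lists among its platelet categories "Confirmed ≥ 30% Platelet count decrease from baseline; further classifying by the lower limit of normal (Above or below". The same section gives one confirmation rule for all its confirmed laboratory rows:

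- Window: "A confirmed value is based on a consecutive lab value performed on a different day to, but within 7 days of, the initial value".
- Better value inside the window: "If the consecutive value is in a better category, then the initial value is confirmed using the consecutive value category".
- No usable second value: "If values that are not confirmed due to failure to retest or missing lab values, then the initial value is presumed confirmed".

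On the schedule, Protocol 8.5.2 says "Platelet count will be monitored every 2 weeks during the Treatment Period" and then lists "Study Days 85, 92, 106, 120, 148, and 169" for the Post-Treatment Period. Appendix A gives visit windows of ±2 days through Day 106 and ±5 days for Days 120, 148 and 169.

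On retesting, Protocol 8.5 requires confirmation, ideally within 3 days, of results that meet the safety monitoring criteria. For platelets, 8.5.2 and Table 5 set these as absolute counts. Above 100,000/mm³ the table asks for no action and the routine schedule only. No protocol rule is triggered by a relative fall.

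**The concern.** A 7-day window makes sense where the protocol orders a prompt second sample. The other confirmed rows (ALT/AST, potassium, eGFR, UPCR and the absolute platelet bands) rest on such criteria. For them the presumed-confirmed default is a conservative backstop for a missed retest. Protocol 8.6.1 uses a similar default for the liver stopping rules.

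The relative platelet row has no such trigger, so the backstop becomes the normal route into the table. The row can then fail in either of two directions, depending on how the default is read:

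- **Literal reading.** A patient at 250,000 at baseline, 170,000 on Day 15 (a 32% fall) and 250,000 on Day 29 is reported as confirmed.
- **Narrow reading.** If a failure to retest means only a missed required retest, a patient at 170,000 on Days 15, 29 and 43 is never confirmed, because no two of those counts lie within 7 days.

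Two programmers could therefore build different tables from the same data. This row is also the only categorical platelet summary that reaches above 100,000/mm³, so a reader would look there for individual patients with reproducible relative falls.

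**Working it through.** The plan states no expected incidence for this row, so there is no figure to reproduce. The check has three parts.

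**1. Gaps between scheduled post-baseline counts.** The minimum gap is the nominal gap minus both visit windows; the maximum is the nominal gap plus both.

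| Pair | Nominal (days) | Minimum | Maximum |
|---|---|---|---|
| D15–29, 29–43, 43–57, 57–71, 71–85 (each) | 14 | 14 − 2 − 2 = 10 | 14 + 2 + 2 = 18 |
| D85–92 | 7 | 3 | 11 |
| D92–106 | 14 | 10 | 18 |
| D106–120 | 14 | 14 − 2 − 5 = 7 | 14 + 2 + 5 = 21 |
| D120–148 | 28 | 18 | 38 |
| D148–169 | 21 | 11 | 31 |
| D120–169, if no D148 count | 49 | 39 | 59 |

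None of the five intervals from Day 15 to Day 85 can be 7 days or less. Nominally 1 of 10 intervals qualifies (1 of 9 without Day 148). Days 106 and 120 reach exactly 7 days only at the extreme of both windows. Day 148 is listed in Protocol 8.5.2, but the Appendix A hematology row as extracted shows no mark there. That may be an extraction fault and does not alter the result.

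**2. When a 30% fall escapes the retest rules.** The count stays above 100,000/mm³ when 0.70 × baseline > 100,000, that is, when baseline > 100,000 / 0.70 ≈ 142,900/mm³. For example, 200,000 × 0.70 = 140,000 triggers no extra count. Eligibility requires a screening count of at least 125,000. From a baseline between 125,000 and about 142,900, any 30% fall reaches 100,000 or below and does trigger closer monitoring, so the 7-day rule works there. Larger falls from higher baselines can also cross that line.

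**3. Illustrative size.** The simulated patients have no true platelet change, a log-normal baseline and ten independent log-normal post-baseline counts (D15, 29, 43, 57, 71, 85, 92, 106, 120, 169). A dip is a count ≤ 0.70 × baseline. The within-person CV is an assumption; the documents give none.

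- Rule as written (literal): any dip counts, except that a Day 85 dip also needs a low Day 92.
- Comparator: the next scheduled count must also be low; only a Day 169 dip is presumed.

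| Assumed CV | As written | Next count must agree |
|---|---|---|
| 8% | 0.6% | 0.1% |
| 10% | 3.8% | 0.9% |
| 15% | 21.7% | 7.8% |

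Separate runs differ by a few tenths of a point at most. With about 150 / 3 = 50 patients per group, CV 10% gives 50 × 0.038 ≈ 1.9 patients against 50 × 0.009 ≈ 0.4. CV 15% gives 50 × 0.217 ≈ 10.9 against 50 × 0.078 = 3.9. The comparator is close to the fix below but not identical, since the fix moves Day 120 dips without a timely follow-up count to a separate line.

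**The case against.** **Presuming confirmation is the cautious choice in a safety table.** This is a fair point. It argues against a remedy that discards events, and the fix below discards none. It does not justify labelling as confirmed a fall that the next scheduled count did not support.

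**The rule need not hide a drug effect.** A reader might infer that false confirmations in every arm mask a true difference. The documents do not support that: they say nothing about the pattern of any platelet effect, and the answer depends on it. Take a uniform 15% true fall from Day 15 to Day 92 at CV 12% (both assumed). The row as written then flags 38% against 10% in patients with no change, while requiring the next count to agree gives 14% against 3%. Approximate power at 50 per arm is 94% and 55%. For that pattern the stricter rule loses signal; it does better if only a minority have large sustained falls.

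**An unlimited follow-up interval would be unsafe.** This stands. If any later count could overturn a dip, a Day 169 count could cancel a Day 120 dip 49 days earlier, when recovery off drug is plausible given the stated half-life of about 2 to 4 weeks. The window must be bounded.

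**Other displays remain.** By-visit change and percent change are summarised and listings are provided. Unscheduled and local results also count in the abnormality tables if drawn (SAP 3.2.1 and 3.7.3). This limits the damage, but those displays do not count patients with a reproducible fall, and nothing requires the extra draws.

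**A normal count two weeks later does not prove the dip was unreal.** Agreed. It is, however, the only scheduled follow-up evidence, and the rule ignores it.

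**Conclusion.** The point holds for falls of at least 30% that leave the count above 100,000/mm³. There the 7-day window has almost no scheduled counts to act on. The row either labels unsupported single dips as confirmed or, on the narrower reading, misses sustained falls. The schedule arithmetic and the ambiguity rest on the documents alone.

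The size does not. The figures of 0.6%, 3.8% and 21.7% against 0.1%, 0.9% and 7.8% assume CVs of 8%, 10% and 15%, independent errors, no true change and the literal reading.

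The scope is one descriptive safety row. A reader might connect it to the platelet adverse event of special interest, but that event is defined by counts below 50,000/mm³ with bleeding or below 25,000/mm³, and is captured on the CRF. It is unaffected, as are the stopping rules, the absolute platelet bands and every efficacy analysis. The same rule applies in all arms, so it does not by itself favour one. The correction is still worth making, because the row gives a wrong or undefined result as written and the change is small.

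**What to change.** In SAP 3.7.3, for the ≥ 30% platelet-decrease row only:

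- Count a fall as confirmed if the next available platelet count on a later day, scheduled or unscheduled and within about 18 days, also shows a decrease of at least 30%. Eighteen days is the 14-day interval plus two 2-day windows.
- Count it as not confirmed if that next count does not.
- If no count falls in the window (typically after Day 120 or Day 169, or if Day 120 is drawn late after Day 106), report the patient on a separate line as presumed confirmed with no follow-up count.
- Also show the number of patients with any single decrease of at least 30%, so that no event is lost.

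Keep the 7-day rule for the rows where the protocol asks for a retest. No clinical monitoring changes and no new data are needed. The cost is a short SAP edit, a small programming change, one or two extra table lines, and a footnote explaining that this row uses a different confirmation interval from the others.

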8.5. Safety Monitoring Rules

Please refer also to the 'Guidance for Investigator' section of the Investigator's Brochure.

For the purposes of safety monitoring Baseline is defined as:

• The last non-missing measurement prior to the first dose

In addition to the standard monitoring of clinical safety parameters, the following guidelines are provided for the monitoring of selected parameters chosen based on preclinical and clinical observations.

Confirmation Guidance: At any time during the study (Treatment or Post-Treatment Periods), the initial clinical laboratory results meeting the safety monitoring criteria presented below **must be confirmed** by performing measurements (ideally in the same laboratory that performed the initial measurement) on new specimens. All new specimen collections should take place as soon as possible (ideally within 3 days of the initial collection). For stopping rules, if the initial laboratory result is observed during the Treatment Period, the results from the retest **must be available** prior to administering the next dose of Study Drug (ISIS 757456 or placebo).

Re-dosing Guidance: Patients with initial laboratory test values that reach a stopping rule must not be re-dosed until the re-test results are available. In general, patients who do not meet the stopping rules based upon retest may continue dosing. However, the Investigator and the Sponsor Medical Monitor (or appropriately qualified designee) should confer as to whether additional close monitoring of the patient is appropriate. If any of the stopping criteria described below (refer to Sections 8.6.1 to 8.6.6) are met, the patient will be permanently discontinued from further treatment with Study Drug (ISIS 757456 or placebo), evaluated fully as outlined below and in consultation with the Sponsor Medical Monitor or appropriately qualified designee, and will be followed up in accordance with Section 8.8 of the protocol.

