8.5.4. Safety Monitoring for Potassium

In the event of a potassium measurement > 5.3 mmol/L at any time during the study (Treatment or Post-Treatment Period), the initial measurement(s) should be confirmed. If the initial potassium measurement is confirmed to be > 5.3 mmol/L, weekly monitoring will be initiated until levels return to < 5.3 mmol/L.

In the event of a potassium measurement ≥ 5.5 mmol/L, but less than 6.0 mmol/L, study drug is to be held. In the event of a potassium measurement ≥ 6.0 mmol/L refer to Section 8.6.5 Stopping Rule for Potassium. In the event of a potassium measurement ≥ 5.5 mmol/L, the Investigator or designee should assess for symptoms consistent with hyperkalemia (e.g., muscle weakness or paralysis). An ECG may be considered per Investigator judgement to assess electrocardiographic signs of hyperkalemia (delayed conduction, heart block, arrhythmias) which, if conducted, should be discussed with the Sponsor Medical Monitor or designee to determine continued dosing with Study Drug. The investigator or designee should consider treating the patients with therapies that reduce the serum potassium, such as a low-potassium diet, diuretics, or a reduction or cessation of medications that can increase the serum potassium (ACEi/ARB). Serum potassium should be measured frequently until documented to be < 5.5 mmol/L. Dosing with Study Drug may continue after a confirmed potassium measurement < 5.5 mmol/L with Investigator and Sponsor Medical Monitor or designee consultation.

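### Both potassium rows in SAP 3.7.3 count confirmed values only, so a high value retested lower on another day within 7 days is dropped or moved down, even if treated in between

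*Combined protocol and SAP*

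**What the plan says.** SAP 3.7.3 tabulates the number and percentage of subjects in two potassium categories, 5.5 to < 6 mmol/L and ≥ 6 mmol/L, both restricted to confirmed values and both using central and local results. Five rules in the same section decide who is counted:

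- Timing: "A confirmed value is based on a consecutive lab value performed on a different day to, but within 7 days of, the initial value".
- A lower retest: "If the consecutive value is in a better category, then the initial value is confirmed using the consecutive value category".
- No retest: "If values that are not confirmed due to failure to retest or missing lab values, then the initial value is presumed confirmed".
- Several results on one day: "then the worst value will be utilized in the analysis".
- Several confirmed values in one subject: "Subjects with more than one confirmed value will be counted exactly once under the worst confirmed category".

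On the protocol side, section 8.5.4 acts on a measurement without waiting for a second one: "In the event of a potassium measurement ≥ 5.5 mmol/L, but less than 6.0 mmol/L, study drug is to be held". At ≥ 5.5 mmol/L it also asks the investigator to consider measures that lower potassium, including reducing or stopping an ACE inhibitor or ARB. Section 8.6.5 stops study drug permanently at a confirmed value ≥ 6.0 mmol/L. The confirmation guidance in section 8.5 asks for a new specimen and sets only this timing: "All new specimen collections should take place as soon as possible (ideally within 3 days of the initial collection"). It does not require a different day.

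**The concern.** A confirmation rule is meant to remove spurious first values. This one cannot tell a spurious value from a real one that was treated before the retest. Both give a high result followed by a lower one, and in both the subject takes the lower category. Because the table has no row below 5.5, the subject may then not be counted at all. A patient who was acted on and promptly retested can leave the table, while a patient with the same first value and no retest stays in it.

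Hyperkalaemia is one of the risks of RAAS blockade named in protocol Table 1. Amendment 4 opened the trial to patients on potassium-sparing diuretics and to eGFR down to 30 mL/min/1.73 m². The arms are small: 150 patients split 1:1 into cohorts and 2:1 within each give about 50 per active dose and 50 on pooled placebo. One or two uncounted patients can change how an arm reads.

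**Working it through.** The documents state no expected hyperkalaemia rate or precision, so there is no figure of the plan's own to reproduce. The check applies the rule to example sequences.

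**1. The rule as a formula.** Take the worst potassium on each tested day and give it a category: none (< 5.5), 5.5 to < 6, or ≥ 6. Pair each day with the next tested day if that falls within 7 days.

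Category for the day = the lower of (its own category, the next tested day's category). With no such next day, the day keeps its own category; this reads a gap of more than 7 days as failure to retest. The subject takes the highest category over all days.

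**2. Applied to examples (mmol/L).**

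| Sequence | SAP 3.7.3 | Worst post-baseline value |
|---|---|---|
| 6.3, then 5.1 two days later | not in table | ≥ 6 |
| 5.8, then 5.2 two days later | not in table | 5.5 to < 6 |
| 6.3, then 5.7, then 5.0 | 5.5 to < 6 | ≥ 6 |
| 5.8, then 6.2, then 5.0 | 5.5 to < 6 | ≥ 6 |
| 6.3, then 6.1 | ≥ 6 | ≥ 6 |
| 6.3, no retest within 7 days | ≥ 6 | ≥ 6 |
| 6.3, same-day 5.1, nothing further within 7 days | ≥ 6 | ≥ 6 |

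A subject is lost only if the next value is on another day, within 7 days and below 5.5.

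**3. Same-day confirmation.** Take 6.2, a second specimen the same day at 6.1, then 5.3 the next day. Protocol 8.5 does not bar the second specimen from confirming the first, so 8.6.5 can be met. Under the SAP the two same-day results reduce to 6.2, the next day's 5.3 sets the category, and the patient is in neither row.

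**4. How far a fall between draws matters.** Assumptions not in the documents: the retest is Normal(initial − fall, SD), SD is 0.2 to 0.3, and the fall from treatment or holding drug is 0.5 to 0.8. Values are reported to 0.1, so the cuts are 5.45 and 5.95.

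- Initial 5.8, no fall: P(retest < 5.5) = Φ((5.45 − 5.8)/SD) = Φ(−1.75) to Φ(−1.17) = 0.04 to 0.12.
- Initial 5.8 with a fall: from Φ((5.45 − 5.3)/0.3) = 0.69 to Φ((5.45 − 5.0)/0.2) = 0.99.
- Initial 6.2 with a fall, leaving the ≥ 6 row: from Φ((5.95 − 5.7)/0.3) = 0.80 to Φ((5.95 − 5.4)/0.2) = 1.00.
- Initial 6.2 with a fall, leaving both rows: from Φ((5.45 − 5.7)/0.2) = 0.11 to Φ((5.45 − 5.4)/0.2) = 0.60.

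On these inputs, measurement noise alone rarely moves 5.8 out of the table; a real fall usually does.

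**5. Effect on counts per arm.** Also assumed: 50 per arm, a share p = 4% to 10% with any value ≥ 5.5, and a share q = 25% to 75% of those retested below 5.5 within 7 days.

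- Any post-baseline value: 50p = 2.0 to 5.0 expected. P(no case) = (1 − p)^50 = 13% down to 0.5%.
- SAP rule: 50p(1 − q) = 0.5 (p = 4%, q = 75%) to 3.75 (p = 10%, q = 25%). P(no case) = (1 − p(1 − q))^50 = 60% down to 2%.

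**The case against.** **Confirmation has a purpose.** Protocol 6.2 names haemolysis as a cause of uninterpretable results, 8.6.5 itself speaks of a confirmed value, and 8.5 lets patients who do not meet a stopping rule on retest generally continue. A 6.2 retested lower is therefore not automatically a stopping-rule case. This stands, and is why the confirmed rows should stay. Only the same-day sequence in step 3 is a true mismatch with the stopping rule, and the documents do not say how often same-day repeats occur.

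**Other outputs remain.** A reader might infer that these cases vanish from all reporting. They do not.

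- Protocol 9.3.1 counts as an adverse event a laboratory deterioration that changes study or concomitant treatment, which describes most of the cases at issue. They should then reach the TEAE tables and, where drug is stopped, the discontinuation table.
- SAP 3.7.2 adds a hyperkalaemia incidence summary.
- By-visit chemistry and listings do not depend on confirmation.

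None of these assures the count. Results judged not clinically significant are not reported as adverse events (protocol 9.5.1). The SAP 3.7.2 summary has no stated definition. By-visit tables leave out unscheduled results and average results sharing a visit label (SAP 3.2.1). Listings give no incidence by arm.

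**Net direction.** A reader might also infer that potassium is counted only after a different-day retest, and that the table must understate harm. The first is wrong, because values never retested are presumed confirmed. The second is not established: that same presumption can count spurious values. What is certain is narrower. The number of patients placed at ≥ 5.5 by this rule can never exceed the number with any such value, and may be smaller for reasons unrelated to whether the first value was real.

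**Conclusion.** The concern holds in a limited form. In SAP 3.7.3 a potassium value ≥ 5.5 mmol/L followed by a different-day value below 5.5 within 7 days is not counted, and a value ≥ 6 followed by 5.5 to < 6 is moved down. This applies even when the retest follows the response protocol 8.5.4 foresees. The SAP's different-day requirement also does not match protocol 8.5. No unconfirmed potassium row is planned, although the same section has an at-any-time row for ALT or AST with bilirubin.

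The existence of the gap follows from the text alone. Its size does not: the documents give no rate of hyperkalaemia, no share treated and no fall between draws, and treatment is only to be considered. The ranges in steps 4 and 5 illustrate what the rule could do and are not forecasts. It is a worthwhile, inexpensive correction to the by-arm incidence of a named risk, not a flaw in the trial's main inference.

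**What to change.** In SAP 3.7.3, keep the two confirmed rows and add two more: subjects with any post-baseline potassium ≥ 5.5 mmol/L, and subjects with any ≥ 6.0 mmol/L, regardless of confirmation. Use central and local, scheduled and unscheduled results, and leave out samples reported as uninterpretable. State how the hyperkalaemia summary in SAP 3.7.2 is defined (adverse event terms, a laboratory threshold, or both).

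The SAP's different-day rule for potassium and the confirmation guidance in protocol 8.5 must be reconciled, so that a patient who meets 8.6.5 cannot be missing from the table that reports it. The definition of confirmed is shared with ALT/AST, platelets, eGFR and UPCR, so the text should say whether any change applies to potassium alone.

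A rule that stops retests taken after treatment from lowering the category is not recommended. It would need draw times matched to treatment and medication changes, and the added rows make it unnecessary.

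The cost is a few lines of SAP text and two table rows from data already collected. The added rows will include some spurious values, which showing them beside the confirmed rows makes visible. No clinical rule changes.

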8.6.1. Stopping Rules for Liver Chemistry Elevations

In the event of laboratory results meeting the following criteria, and the event is without an alternative explanation as discussed with the Sponsor Medical Monitor, dosing of a patient with Study Drug (ISIS 757456 or placebo) will be stopped permanently; values that are not confirmed due to failure to retest or missing lab values will be presumed confirmed:

- 1. ALT or AST $> 8 \times ULN$, which is confirmed
- 2. ALT or AST > $5 \times ULN$, which is confirmed and persists for ≥ 2 weeks
- 3. ALT or AST $> 3 \times$ ULN, which is confirmed and total bilirubin $> 2 \times$ ULN or INR > 1.5
- 4. ALT or AST > 3 × ULN, which is confirmed, **and** the new appearance (i.e., onset coincides with the changes in hepatic enzymes) of fatigue, nausea, vomiting, right upper quadrant pain or tenderness, fever, rash, and/or concomitant eosinophilia (> ULN)

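### The once-only counting rule in SAP 3.7.3 conflicts with its overlapping liver rows and leaves the ≥ 30% platelet-decline row unclear

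*Combined protocol and SAP*

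**What the plan says.** SAP 3.7.3 (Laboratory Measurements) introduces the liver table as "the number and percent of subjects with post-Baseline results falling in each of the following categories". Its first two rows are "ALT or AST $> 3 \times ULN$, confirmed" and "ALT or AST $> 5 \times ULN$, confirmed". The third adds total bilirubin above 2 × ULN to a transaminase above 3 × ULN and ends "ULN, confirmed or INR > 1.5". The fourth starts "ALT > 3 × ULN at any time during post-baseline", pairs either transaminase above 3 × ULN with bilirubin above 2 × ULN, and does not require confirmation.

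Potassium has two bounded rows. Platelets have four bounded count rows and one relative row for a fall of at least 30%: "Platelet count decrease from baseline; further classifying by the lower limit of normal (Above or below". Two further rows cover a 30% eGFR decline and UPCR of at least 1000 mg/g.

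After the confirmation rules, which compare a repeat value with the initial one as same, worse or better, the section closes with "Subjects with more than one confirmed value will be counted exactly once under the worst confirmed category". It does not say whether this applies per analyte, per list or across the section, nor which row is worst when rows are not on one scale.

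**The concern.** A table that counts patients in each category and a rule that counts each patient in one category agree only when the categories are exclusive and ordered. The liver rows are neither. The row labelled > 3 × ULN would then report something narrower than its label, with no note to tell the reader. Two programmers could also produce different liver tables from the same data by ranking the rows differently. What is at stake is the reported incidence by arm of liver abnormalities and of relative platelet decline. These are safety results of a dose-finding trial that includes a dose not used in the earlier studies the protocol describes.

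**Working it through.** The plan states no figure on this point to reproduce. The check compares row membership with the counting rule and adds short arithmetic.

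**1. Where the rule works.** The potassium rows are ≥ 5.5 to < 6 and ≥ 6 mmol/L. The platelet count rows are 75,000 to ≤ 100,000, 50,000 to < 75,000, 25,000 to < 50,000, and < 25,000/mm³. No value falls in two rows and the order is plain, so once-only counting loses nothing.

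**2. Nested liver rows.** Suppose a patient has a confirmed 4 × ULN and later a confirmed 6 × ULN. There is more than one confirmed value, so the rule applies; the worst category is > 5 ×, and the patient leaves the > 3 × row. Several confirmed values are to be expected in such patients, because Protocol 8.5.1 requires retesting at least weekly after a confirmed value above 3 × ULN.

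**3. Crossing liver rows.** I read row 3 in line with criterion 3 of Protocol 8.6.1, where a transaminase above 3 × ULN "which is confirmed and total bilirubin" above 2 × ULN, or INR above 1.5, is one criterion. Row 3 is then a subset of row 1 and cuts across row 2. A patient at 6 × ULN with INR above 1.5 meets rows 1, 2 and 3, and nothing ranks row 2 against row 3.

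**4. Hypothetical illustration (not trial data).** Take five patients, each with several confirmed values. Their confirmed peaks are 3.5, 4.0, 4.5 (with the bilirubin/INR criterion), 6.0, and 9.0 (with the bilirubin/INR criterion) × ULN.

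| Counting | > 3 × | > 5 × | > 3 × plus bilirubin/INR |
|---|---|---|---|
| Every row met | 5 | 2 | 2 |
| Once, combined row ranked worst | 2 | 1 | 2 |
| Once, > 5 × ranked worst | 2 | 2 | 1 |

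The > 3 × row falls from 5 to 2 under either ranking, and the other two rows depend on the ranking chosen. Adding the three rows recovers the > 3 × total (2 + 1 + 2 = 5; 2 + 2 + 1 = 5), but only for a reader who knows they were made exclusive. The > 5 × total cannot be recovered when the combined row ranks worst, because that row then mixes 4.5 × and 9.0 ×.

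**5. Platelets.** The screening floor is 125,000/mm³ (Protocol 5.2, exclusion 16f).
- 125,000 × 0.70 = 87,500, so from that baseline every count ≤ 87,500 is a fall of at least 30%.
- 1 − 75,000/125,000 = 40%, so every count below 75,000 is a fall of more than 40%.
- 100,000/0.70 ≈ 142,900, so from a baseline at or above this every count ≤ 100,000 meets the relative row.

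The overlap is therefore wide. If the rule is applied across both kinds of row, a patient with several confirmed values loses either the count row or the relative row. Which one again depends on a ranking that is not given.

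**6. Size per patient.** Each active arm has 150 × 1/2 × 2/3 = 50 patients, and pooled placebo has 150 × 1/3 = 50. One patient is 1/50 = 2 percentage points. If all five hypothetical patients were in one arm, the > 3 × row would show 2/50 = 4% instead of 5/50 = 10%.

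**The case against.** The strongest reply is that the rule is narrower than it first looks, and much of that stands.

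- **Trigger.** The rule covers only subjects with more than one confirmed value. A patient with a single confirmed count of 60,000/mm³ has one value meeting two rows, and the instruction to count in each category then governs. A reader might infer that every patient in the low platelet bands must be dropped from a row. The arithmetic shows overlap, not removal.
- **Renal rows.** A reader might also infer that a patient with both an eGFR decline and proteinuria loses one row. That needs the rule to run across two different tests. The same/worse/better confirmation logic makes sense only within one test and points the other way.
- **Combined liver cases.** They do not vanish. The any-time row is not a confirmed row, so transaminase-plus-bilirubin cases remain visible there. It has no INR arm, however, so a patient who qualifies on INR alone is not kept visible by it.
- **Ranking.** Protocol 8.6.1 makes the combined criterion a stopping criterion on confirmation, whereas > 5 × ULN must also persist for at least 2 weeks. This hints that the combined row is worse. It does not resolve the problem, because the > 5 × row then loses those patients.
- **Consequences.** Stopping rules are applied to laboratory results before dosing, not from these tables. Laboratory listings and by-visit summaries are planned, and platelet events of special interest are summarised separately. No renal, hepatic or platelet stopping rule was met in the two earlier Phase 2 trials, although those were shorter and did not use 120 mg. Few patients may be affected. None of this corrects a threshold row that reports less than its label says.

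**Conclusion.** The point holds for the liver rows. For patients with more than one confirmed value, the once-only rule contradicts the instruction to count in each category. It undercounts the > 3 × ULN row and leaves the split between > 5 × ULN and the combined row to an unstated ranking. For the ≥ 30% platelet-decline row it holds conditionally, if the rule is applied across the relative and absolute rows; the SAP neither says so nor excludes it. The eGFR and UPCR rows need only a clarifying phrase.

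The size is 2 percentage points per displaced patient at 50 per arm. This is a unit, not an expected distortion, since the documents give no basis for predicting how many patients will be affected. The platelet figures assume a baseline at the screening floor or above; the analysis baseline is the last pre-dose value and could differ from the screening value.

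It would go too far to say that the trial's stopping thresholds are misreported as a whole. A transaminase above 3 × ULN alone triggers monitoring under Protocol 8.5.1, and a 30% platelet fall is neither a monitoring nor a stopping criterion in Protocol 8.5.2, 8.6.3 or Table 5. The platelet stopping bands are exclusive, and the rule is sound for them.

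**What to change.** Replace the closing sentence of SAP 3.7.3 with one that does three things:

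- applies once-only counting per analyte, and only within the potassium bands and the four absolute platelet bands;
- counts each patient once in every liver row whose criterion is met, and separately in the ≥ 30% platelet-decline row where that criterion is met;
- labels the nested liver rows as cumulative in the table shell.

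The per-analyte wording settles the eGFR and UPCR rows, which should be counted independently.

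The cost is one sentence and a table-shell change, with no new data. The downside is that rows will no longer add up to the number of affected patients and some counts will rise; a footnote can say so.
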